## 9.7.2 Missing, unused, or incorrect data (including dropouts and withdrawals) and unreasonable data

All missing, unused or incorrect data (including dropouts and withdrawals) and unreasonable data will be discussed and finally determined by the investigators and biostatistician in the data review stage. The basic statistical principles for the processing of these data are as follows:

- (1) The details of each drop-out case shall be described, and the drop-out between the test group and the control group shall be compared using Pearson  $X^2$  test or Fisher exact test;
- (2) Missing data at baseline shall not be estimated;
- (3) Missing values of main evaluation indicator (success rate of device cutting and anastomosis) shall not be estimated;
- (4) Missing values of secondary evaluation indicators shall not be estimated;
- (5) The wrong and unreasonable data shall be regarded as missing values;
- (6) Missing values for all safety measures shall be estimated using the worst case;
- (7) Sensitivity analysis shall be performed on the safety data set for all the safety evaluation indicators after treatment.

## 9.8 Procedures for Reporting Deviations from Original Statistical Plan

In general, only the statistical analysis contents pre-specified in the statistical analysis plan can be presented in the clinical trial report of this trial. The increased need for statistical analysis due to various indeterminate reasons will be considered exploratory only.

## 9.9 Selection Criteria and Reasons for Subjects Included in Analysis

- (1) Full analysis set (FAS): According to the basic principles of intention to treat analysis, all the subjects who have received at least one treatment with the investigational medical device and had at least one post-baseline observation data are included in the FAS. The FAS will be used as the primary population for baseline data (and efficacy evaluation) in this study.
- (2) Per-protocol set (PPS): It refers to the subjects in the FAS who do not seriously deviate from the trial

protocol, have good compliance and have no missing primary efficacy indicators. The PPS will be used as the primary population for efficacy analysis in this study.

(3) Safety set (SS): All subjects who have received at least one treatment with the investigational medical device and had at least one safety evaluation. The SS will be used as the primary population for safety analysis in this study.

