#### 8.1.3 Selection of test method and reasons

This clinical trial is a "prospective, multi-center, stratified-block randomization, incomplete blinding, parallel positive control, non-inferiority test".

- (1) Prospective: A research method that tracks from the present to the future. Prospective studies can clarify the causal relationship; uniform diagnostic, detection, and evaluation criteria can be available for the obtained data, the data processing therefore is controllable.
- (2) Multi-center: 5 clinical trial institutions were selected to conduct this clinical trial. The application of multi-center trial can allow to obtain more cases than those of single-center trial in the same time, the clinical trial time therefore can be shortened; since the multi-center trial is completed by different regions, different trial centers and many clinical researchers, the conclusion therefore is often widely representative.
- (3) Stratified block randomization: This trial adopts the stratified block randomization method (with the study site as the stratification factor) and the randomization envelope to randomize the subjects who are screened successfully. The randomized-grouping time is that before the surgery. Randomized grouping ensures that, except for treatment factors, other non-treatment factors that may have confounding effect are kept consistent in each group as far as possible, so as to ensure the balance of baseline of each group; randomized-grouping allows each subject to have equal opportunity to be assigned to the test group or control group.
- (4) Incomplete blinding: Since the investigational medical device and the control medical device are different in appearance, while the subjects are under anesthesia during the operation, the grouping arrangement can not be known. Therefore, the method of incomplete blinding is used, that is, the investigators knows the grouping result, while the subject does not know the grouping result. Blinded data review is also required at the same time. Incomplete blinding can minimize the bias caused by "placebo effect", and make the evaluation of adverse reactions by subjects more objective.

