#### 9.4 Expected Dropout Rate

Version No.: 1.1/Version date: 20190325 Clinical Trial on Performance and Safety of Disposable Powered Articulating Endoscopic Linear Cutter Stapler in Total-Thoracoscopic Anatomic Lobectomy (segmentectomy)

A 20% dropout rate is expected during sample size estimation.

This drop-out rate refers to the proportion of subjects who finally can not be included in the primary analysis. Drop-out subjects refer to those confirmed by the principal investigator with serious protocol violation (affecting the main evaluation/efficacy evaluation). The following conditions may be included, but not limited to: the subject violates the inclusion and exclusion criteria; the subject does not receive any study device; the subject receives the concomitant medication/device prohibited by the protocol; the data of main evaluation indicators are missing; the subject fails to obtain any data after randomization; the subject fails to complete the follow-up visit according to the regulations.

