## 24. Supplementary Provisions

Meanings of the academic terms involved in this study protocol:

**Medical device clinical trial institution:** it refers to the medical institution undertaking medical device clinical trial recognized by NMPA (original CFDA) and NHFPC. Unless otherwise specified, "clinical trial institution" in this protocol refers to "medical device clinical trial institution".

**Investigational/study medical device:** it refers to the medical device to be applied for registration whose safety and effectiveness are confirmed or verified in the clinical trial.

**Sponsor:** it refers to the institution or organization initiating, managing and providing financial support for the clinical trial.

**Investigator:** it refers to the person responsible for conducting the clinical trial in the clinical trial institution. If a trial is conducted by a team of individuals at a clinical trial institution, the investigator is the responsible leader of that team, also known as the principal investigator.

**Ethics Committee:** it refers to an independent institution set by the clinical trial institution to review the scientificity and ethicality of the medical device clinical trial project.

**Management department of medical device clinical trial:** it refers to the division or department set within a clinical trial institution to be responsible for the organization management and quality control of the medical device clinical trial.

**Multi-center clinical trial:** it refers to the clinical trial conducted in more than three (including three) clinical trial institutions in accordance with the same clinical trial protocol.

**Subject:** it refers to an individual recruited for the clinical trial of a medical device.

**Informed consent:** it refers to the process that the subject voluntarily participates in the clinical trial after being informed of all aspects of the clinical trial, as evidenced by the signed and dated informed consent form.

**Informed consent form:** it refers to the supporting document for the subject voluntary participation in the clinical trial.

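### The FAS and safety set are tied to receipt of the device being registered, which as written leaves out ordinary controls; read as either device, they still drop subjects operated on without stapler use

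*Combined protocol and SAP*

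**What the plan says.** Section 9.9 defines three sets.

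- **FAS.** Introduced with "According to the basic principles of intention to treat analysis", it then admits only "all the subjects who have received at least one treatment with the investigational medical device and had at least one post-baseline observation data".
- **PPS.** This set is nested in the FAS ("It refers to the subjects in the FAS who do not seriously deviate from the trial"), so it inherits the FAS entry rule.
- **Safety set.** "All subjects who have received at least one treatment with the investigational medical device and had at least one safety evaluation".

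Section 24 explains the term on which these rules turn: "it refers to the medical device to be applied for registration whose safety and effectiveness are confirmed or verified in the clinical trial". That is the sponsor's stapler. Sections 8.1.3(4), 8.1.5, 8.2.6, 15.1 and 18 name the control device as a separate item, and 8.2.6 assigns the study device to the test group and the control device to the control group.

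On timing, 8.1.3(3) states: "The randomized-grouping time is that before the surgery". Section 8.2.2 places randomisation on the day of the operation. Sections 8.1.3(4) and 8.2.4 say the investigators know the allocation. Section 9.4 lists, among subjects who cannot enter the primary analysis, the case where "the subject does not receive any study device".

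**The concern.** An intention-to-treat set should depend on randomisation and not on what happens in theatre afterwards. Here entry turns on device use, which follows randomisation and is decided by a surgeon who knows the arm.

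Two separate problems follow. The first is the device term: taken with the protocol's own definition, it admits subjects by receipt of the test stapler and leaves the control arm without a rule. The second remains if the term is read as either device. A subject randomised and operated on, but in whom no stapler was used, is absent from the FAS and safety set, and therefore from the PPS.

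Section 14.1.5(37) foresees battery or motor failure that makes the device unusable, with conversion or replacement of the device as possible responses. Section 8.1.7.1 scores a conversion caused by the stapler as a primary endpoint failure. The set definition can therefore remove some of the failures that the endpoint is meant to count. Conversions before first firing would also be missing from the conversion rate (8.1.7.2) and from adverse event counts based on the safety set.

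**Working it through.** **1. Sample size, to confirm that it is not affected.** Inputs from 9.2.1: success 97% in both arms, margin 10 percentage points, one-sided alpha 0.025, power 80%, dropout 20%.

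- n3 = 2 × 0.97 × 0.03 × (0.8416 + 1.9600)² / 0.10² = 45.68
- n4 = 45.68 × {1 + [1 + 4/(0.10 × 45.68)]^½}² / 4 = 64.12, rounded up to 65
- 65 / 0.80 = 81.25, rounded up to 82 per group, 164 in total

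The plan's 65, 82 and 164 all reproduce. Rewording 9.9 does not change them.

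**2. Who enters the sets under each reading of 9.9.** A post-baseline observation and a safety evaluation are assumed present.

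| Subject | As written (9.9 with 24) | Read as either device |
|---|---|---|
| Control, control stapler only | Out of FAS, SS, PPS | In |
| Test, control stapler only | Out of FAS, SS, PPS | In FAS and SS |
| Control, given test stapler | In FAS and SS | In FAS and SS |
| Either arm, operated on, no stapler used | Out of FAS, SS, PPS | Out of FAS, SS, PPS |

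A subject given the wrong device may be removed from the PPS, because 16.1.3(4) lists an incorrect device as a significant deviation where it affects safety or analysis. No section says in which arm a switched subject is analysed. The word treatment is not defined, so it is also unclear whether a device that fails before firing counts.

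**3. Effect on the primary comparison, either-device reading.** All counts are assumed. Controls succeed in 80 of 82. In the test arm three subjects fail after stapler use, and three fail before first use with no stapler fired afterwards. Section 9.7.1 does not name an interval method, so the Wald interval is used:

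lower limit = (p_T − p_C) − 1.96 × √[p_T(1 − p_T)/n_T + p_C(1 − p_C)/n_C]

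- Three dropped: p_T = 76/79 = 0.9620, p_C = 80/82 = 0.9756, difference −0.0136, SE 0.0274. Lower limit −0.0136 − 0.0538 = **−6.7%**, above −10%.
- Three kept as failures: p_T = 76/82 = 0.9268, difference −0.0488, SE 0.0334. Lower limit −0.0488 − 0.0655 = **−11.4%**, below −10%.

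Newcombe limits for the same counts are −8.4% and −12.8%, so the contrast does not depend on the Wald method.

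With fewer failures nothing changes. Two test failures after use and one before use give 79/81 v 80/82, Wald lower limit −4.8%, if the one is dropped, and 79/82 v 80/82, −6.5%, if it is kept.

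**4. Error rate over an assumed range.** Exact enumeration used 82 per arm, control success 97%, true all-randomised test success 87% (at the margin) and the Wald rule. The chance of wrongly declaring non-inferiority is 4.3% when every randomised subject counts. If 1%, 2%, 3% or 5% of test subjects fail before first use and are dropped, with none dropped from control, it is 6.6%, 9.6%, 14.0% or 28.7%.

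**The case against.** The strongest reply is that this is a drafting slip. Sections 9.5 and 9.7.1 compare the two groups throughout, so the sponsor cannot have meant to analyse an empty control arm. Device terms are loose elsewhere too: 8.1.8(7) defines defects by reference to the test device, while 8.1.2 compares defect rates between arms. This stands. A reader might infer that the plan sets out to exclude all 82 controls, or that it deliberately treats the arms differently, and the documents do not support either.

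A reader might also infer that switching staplers could by itself reverse the trial's conclusion. It could not on any single reading. The reading that deletes switched test subjects also empties the control arm, and the either-device reading keeps them. Nor does 8.1.7.1 score a switch as a failure: it looks at the staple lines and at conversions caused by the stapler.

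The conversions in the series cited in 9.2.1 (8 of 160, one due to stapling failure) might be taken as a rate for subjects lost before firing. The protocol gives no timing for them relative to first stapler use, so they support no figure.

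Finally, excluded subjects would not go unseen. Section 9.7.2 requires each dropout to be described and dropouts to be compared between arms, and 8.1.3 calls for blinded data review. Section 9.4 defines dropout for sample size and is not itself an FAS rule. These points limit the harm, but a description of dropouts does not put them back into the primary comparison, the conversion rate or the adverse event rates.

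**Conclusion.** Section 9.9 is wrong as written: with the definition in section 24, ordinary controls qualify for no analysis set. This is most likely unintended, and reading the term as either device removes the asymmetry by device. What remains is that subjects randomised and operated on without stapler use leave the FAS, safety set and PPS because of an event after randomisation, with an unblinded surgeon and under an intention-to-treat label.

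The size is unknown. The documents give no rate of conversion or device failure before first use, and the rate could be zero. The change from −11.4% to −6.7% and the rise in error rate from 4.3% to between 6.6% and 28.7% rest on assumed counts, on losses in the test arm only, and on scoring those subjects as failures. They show that a few such subjects could decide the result. They do not predict that this will happen.

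**What to change.** In 9.9:

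- Define the FAS as all randomised subjects whose operation was started, analysed in the allocated arm whatever stapler was used.
- Define the safety set as the same subjects grouped by the stapler actually used, with those in whom no stapler was fired kept in their allocated arm.
- Replace the investigational-device term with test or control device wherever set membership depends on it.
- State that the no-device ground in 9.4 is not a reason for exclusion from the FAS.

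In 8.1.7.1, state that a device-caused failure or conversion before first firing counts as a primary endpoint failure. For conversions this follows the rule already there. Device failure before firing without conversion is not addressed there and needs to be written down.

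The cost is wording only. The sample size and the randomisation procedure stay as they are. Section 9.1 leaves the SAP open until database lock, so the change can go there as well as into the protocol, and it should be settled before outcomes by arm are reviewed. The one practical demand is that operative and follow-up data be collected for subjects in whom no stapler was used.

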#### 8.1.7 Effectiveness evaluation method

# 8.1.7.1 Main effectiveness evaluation indicators, method and time for evaluation, recording and analysis

#### (1) Success rate of device cutting and anastomosis

**Justification for selection:** Through the mechanical transmission device, the stapler places two or multiple rows of staples prearranged in parallel and staggered rows in the component into the tissues that are aligned and need to be anastomosed. After passing through the tissues, the staples are blocked by the anvil jaw and

bend inward, forming a B-shaped staggered arrangement to anastomose the tissues together. Whether the stapler can successfully cut and staple the lung tissue is very critical to the video-assisted thoracoscopic surgery. If the cutting and stapling of lung tissue fails, the subject may need to be converted into thoracotomy, which will increase the risk of the subject. Therefore, in this clinical trial, the "success rate of device cutting and anastomosis" is selected as the primary endpoint, and the effectiveness of this product is evaluated by calculating the number of subjects required to be converted into thoracotomy due to the stapler.

**Evaluation time:** During the surgery.

Evaluation site: Tissues receiving linear stapler for pulmonary anastomosis.

**Evaluation method:** The transection and anastomosis of lung tissues are performed during the operation. The device is withdrawn after successful triggering. The cutting staple line is carefully checked for integrity, air leakage and bleeding. If all staple lines are complete, without air leakage or bleeding, it is judged that the cutting and anastomosis of the device is successful. If there is persistent air leakage and bleeding at the anastomosis site, and **conversion to thoracotomy is required**, it is judged as device cutting and anastomosis failure.

**Formula:** Device cutting and anastomosis success rate = number of subjects with successful anastomosis in each group/total number of subjects in this group  $\times 100\%$ 

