### 9.5 Qualification/Disqualification Criteria for Clinical Trial Results

The non-inferiority hypothesis is tenable if the lower limit of 95% confidence interval of the difference in the primary effectiveness evaluation indicator "device cutting and anastomosis success rate" between the test group and the control group is greater than the non-inferiority critical value (-10%).

The secondary effectiveness evaluation indicators and safety evaluation indicators are tested by difference test, and the significance level is set at 0.05. If the test result of the difference in any secondary evaluation indicator and safety evaluation indicator between the test group and the control group is p > 0.05, then there is no significant difference in this indicator between the test group and the control group.

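### Two analysis sets are both called primary for efficacy, the success rule names neither, and Section 9.4 could let a stapler failure recorded in surgery drop out of the primary analysis

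*Combined protocol and SAP*

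**What the plan says.** Section 9.9 gives two sets the same role. Of the FAS it says "The FAS will be used as the primary population for baseline data (and efficacy evaluation) in this study". Of the per-protocol set (PPS) it says "The PPS will be used as the primary population for efficacy analysis in this study". It gives no order between them and does not require both to succeed. Apart from serious deviation, PPS members must "have good compliance and have no missing primary efficacy indicators".

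The decision rule in Section 9.5 begins "The non-inferiority hypothesis is tenable if the lower limit of 95% confidence interval of the difference in the primary effectiveness evaluation indicator" and compares that limit with -10%. It names no analysis set. Neither does the primary method in Section 9.7.1, which also does not say how the interval is calculated.

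Section 9.4 explains the 20% allowance: "This drop-out rate refers to the proportion of subjects who finally can not be included in the primary analysis". It continues: "Drop-out subjects refer to those confirmed by the principal investigator with serious protocol violation (affecting the main evaluation/efficacy evaluation". Its list of conditions that may count includes "the subject fails to complete the follow-up visit according to the regulations".

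Section 8.1.7.1 judges the primary endpoint in theatre: "The transection and anastomosis of lung tissues are performed during the operation", and the staple lines are inspected there and then. Section 8.1.8(5) treats staple-line adverse events as serious adverse events (SAEs). Section 8.1.6.9, criterion (3), says a subject with an SAE should be withdrawn.

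**The concern.** There are two linked problems.

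First, if the FAS and PPS results fall on different sides of -10%, the protocol does not say which one stands.

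Second, the primary outcome is known on Day 0, so a missed Day 7 or Day 30 visit cannot change it. Yet a missed visit is listed as a possible reason for leaving the primary analysis. Subjects whose stapler failed are plausibly more likely than others to have incomplete follow-up, because staple-line events are SAEs and SAEs should lead to withdrawal. Section 11.2 itself names too many SAE withdrawals as a way the trial could fail. An exclusion linked to the outcome removes failures from both numerator and denominator logic: the failures go and the successes stay. Both arms then look closer to 100%, which favours non-inferiority. Few failures are expected, so one contested subject can decide a close result.

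**Working it through.** **Inputs.** From Section 9.2.1: success 97% in both arms, margin -10 points, one-sided alpha 0.025, power 80%, 65 evaluable per arm, 82 after 20% drop-out. Not in the documents, and therefore assumed: the share of failures excluded, and true test-arm rates other than 97%. No interval method is named, so each result is given as Newcombe / Wald.

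**The plan's own figure.** n3 = (2 × 0.97 × 0.03)(0.8416 + 1.9600)² / 0.10² = 45.68. With the continuity correction, n4 = 45.68 × {1 + √[1 + 4/(0.10 × 45.68)]}² / 4 = 64.12, so 65. Then 65/0.8 = 81.25, so 82 per arm and 164 in total. The plan reproduces, and the sample size is not in dispute.

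**Limits used.** With observed rates p (test) and q (control):
- Wald lower limit = p − q − 1.96 √[p(1−p)/n₁ + q(1−q)/n₂].
- Newcombe lower limit = p − q − √[(p − l)² + (u − q)²], where l is the Wilson lower limit for test and u the Wilson upper limit for control.

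**One subject, control 80/82** (q = 0.9756, u = 0.9933):
- Newcombe, test 77/82: p = 0.9390, l = 0.8651. Limit = −0.0366 − √(0.0739² + 0.0177²) = −11.3%, fails.
- Newcombe, one test failure left out, 77/81: p = 0.9506, l = 0.8798. Limit = −0.0250 − √(0.0708² + 0.0177²) = −9.8%, passes.
- Wald already passes at 77/82 (−9.82%). Its flip is one failure further on: 76/82 gives −11.43% (fails) and 76/81 gives −9.95% (passes).

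Both methods have tables that one exclusion reverses, but they are different tables.

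**Share of failures removed.** Exact binomial enumeration, 82 per arm, true success 87% test and 97% control (a true difference at the margin). Each failure in either arm is excluded with the same probability.

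| Share of failures removed | Chance of declaring non-inferiority (Newcombe / Wald) |
|---|---|
| 0 | 2.1% / 4.3% |
| 25% | 6.6% / 12.5% |
| 50% | 19.7% / 35.9% |

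Expected failures here are 82 × 0.13 = 10.7 in the test arm and 82 × 0.03 = 2.5 in the control arm, so 50% means losing about five test failures.

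**Probability that the full data fail but the reduced data pass**, control 97%:

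| True test success | One test failure left out | One failure left out of each arm |
|---|---|---|
| 97% | 8.0% / 3.2% | 1.4% / 1.9% |
| 95% | 15.6% / 11.4% | 3.7% / 6.3% |
| 93% | 15.5% / 15.9% | 4.0% / 8.1% |
| 90% | 8.0% / 11.2% | 2.1% / 5.2% |
| 87% | 2.6% / 4.4% | 0.7% / 1.9% |

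The last column counts only tables in which each arm has a failure to remove. If an arm with no failures is instead left unchanged, the 97% row becomes 3.2% / 2.5% and the largest values become 5.3% / 9.5%.

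**The case against.** The strongest reply is that the exclusion route is narrow.

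- Section 9.4 describes a planning allowance. It requires the principal investigator to confirm a serious violation affecting the main evaluation, and its list is only of conditions that may count. A late missed visit does not affect an endpoint settled in surgery.
- The PPS definition mentions neither SAE withdrawal nor follow-up. Section 16.1.1 defines a deviation as not following the protocol, and withdrawal under 8.1.6.9 follows it. Section 16.1.5 says examinations left undone after early discontinuation are not deviations, and 16.1.4 grades missing data that leave the primary result unaffected as minor.
- Not every primary failure need be a staple-line adverse event: Section 14.1.5(37) also foresees battery, motor and reload failures leading to conversion.
- A recorded failure would normally stay in the FAS.
- Section 8.1.3 requires blinded data review, Section 10.4 divides the sets before lock, and 8.1.6.9 asks that whatever can still be evaluated is evaluated.

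Much of this stands, and it makes exclusion possible rather than expected. It does not close the gap. The examples in 16.1.5 are patient decisions, not withdrawal by the investigator. Section 16.1.4 also requires safety results to be unaffected, while staple-line bleeding and infection are assessed to the end of follow-up. The investigators know the allocation (8.1.3) and take part in the data-review decisions (9.7.2). The FAS protects the result only if the FAS decides, which is the point left open.

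Section 9.1 refers to a separate statistical analysis plan to be finalised before lock. Its text was not available, so whether it names the deciding set cannot be checked. The contradiction in the protocol remains either way.

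**Conclusion.** The concern holds; this should be fixed. Section 9.9 contradicts itself on the primary efficacy population, Section 9.5 does not resolve it, and Section 9.4 offers a reason for exclusion that has no bearing on an endpoint decided in surgery.

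That much is read directly from the text. The size of the bias is less certain, because it depends on an assumed share of failures removed. The effect is moderate unless a large share is lost: removing a quarter of failures in both arms roughly triples the chance of a false non-inferiority claim at the margin, under either method. A single test-arm exclusion turns a fail into a pass with probability up to about 16% across the rates examined. With one failure removed from each arm the probability is lower, at most 4.0% (Newcombe) or 8.1% (Wald) on the convention used in the table. These figures illustrate sensitivity and do not forecast what will happen.

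**What to change.** 1. In Sections 9.5 and 9.9, name the one set that decides non-inferiority.
2. State that every recorded intraoperative primary outcome is analysed as recorded in that set, whatever SAE, withdrawal or missed Day 7 or Day 30 visit follows. The one exception is a subject who asks to withdraw and refuses use of earlier data, as Section 8.1.6.9 allows.
3. Remove incomplete follow-up from the Section 9.4 list as a reason for exclusion from the primary endpoint.
4. Reconcile the withdrawal passages. Section 8.1.6.9(3) says subjects with an SAE should be withdrawn. Sections 8.1.6.7 and 14.1.3 ask for adverse events to be observed to outcome, with 14.1.3 also allowing follow-up to the end of the trial. Section 16.1.3(2) makes failure to withdraw a subject who meets discontinuation criteria a significant deviation, without naming SAEs. Which clinical rule applies is for the sponsor and investigators; none is proposed here.

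The cost is wording only. The sample size stays at 164 and no procedure is added. Observed success rates may look slightly less favourable.
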